2. **Clinical Information:** (symptom duration, myelopathic evaluation, motor/sensory evaluation, pain and fatigue level, field of view testing)
3. **Narcotic usage:** recent intake, last intake, current medications, frequency of medication usage

After each trial, patients will receive a post-simulation questionnaire:

Post-trial Questionnaire

1. Participants' self-judged level of safety while driving with three response categories; unsafe (1), moderately safety (4), very safe (7)
2. Participants' self-judged level of comfort while driving with three response categories; uncomfortable (1); moderately comfortable (4); comfortable (7)
3. Participants' self-judged effect of surgery on driving ability with three response categories; made worse (1); no effect (4); improved (7)
4. Participant's belief that the simulator can reproduce real-world driving on a numerical scale of 0 – 10 (0=not realistic, 5=moderately realistic, 10=very realistic)

FDA STATUS OF DRIVING SIMULATOR**FDA Medical Device Definition**

If a product is labeled, promoted or used in a manner that meets the following definition in section 201(h) of the Federal Food Drug & Cosmetic (FD&C) Act it will be regulated by the [Food and Drug Administration \(FDA\)](#) as a medical device and is subject to premarketing and postmarketing regulatory controls. A device is:

- "an instrument, apparatus, implement, machine, contrivance, implant, in vitro reagent, or other similar or related article, including a component part, or accessory which is:
 - recognized in the official National Formulary, or the United States Pharmacopoeia, or any supplement to them,
 - **NOT APPLICABLE TO DEVICE.**
 - intended for use in the diagnosis of disease or other conditions, or in the cure, mitigation, treatment, or prevention of disease, in man or other animals, or
 - **DEVICE CANNOT BE USED TO DIAGNOSE ANY CONDITIONS.**
 - **DEVICE SERVES TO DETECT CHANGES IN DRIVING PERFORMANCE IN A SIMULATED SETTING.**
 - **DEVICE NOT USED FOR CURE, MITIGATION, TREATMENT OR PREVENTION OF ANY CONDITION.**
 - intended to affect the structure or any function of the body of man or other animals, and which does not achieve its primary intended purposes through chemical action

NCT02782923

within or on the body of man or other animals and which is not dependent upon being metabolized for the achievement of any of its primary intended purposes."

- **DEVICE CANNOT AFFECT STRUCTURE OR FUNCTION OF SUBJECTS.**

Given that this device does not meet the criteria for a medical device, the device is exempt from FDA regulations. Furthermore, the STISIM simulator has been validated and used in numerous studies including FDA evaluation of drug performance on driving ability (1).

The U.S. Department of Transportation and National Highway Traffic Safety Administration have similarly conducted many studies using the STISIM simulated environment (2,3). Numerous clinical trials have been conducted using the STISIM simulator(4-8). The number of patients enrolled in these studies ranged from 20-30 subjects per group.

O. DATA ANALYSIS, MONITORING AND STORAGE**1. Types of Data**

- a. Data Accuracy
- b. Protocol Compliance
- c. Recruitment of Subjects
- d. Screen Failures
- e. Safety Monitoring/Management

2. Responsibilities and Roles for Gathering, Evaluating and Monitoring the Data

- a. Principal Investigator and Sub-Investigators:
 1. The principal investigators will be the monitoring entity due to the nature of this study – small number of subjects and the study is conducted only at one site
 2. Responsible for insuring protocol compliance
 3. Responsible for collecting and recording all clinical data pre- and post-operatively
 4. Responsible for monitoring data collected and evaluating the progress of the study, assessments of data quality, retention, and adverse events
 5. Responsible for monitoring safety of research participants from visits with patients
 6. Responsible for stopping or modifying protocol if needed
 7. Responsible for intraoperative data collection
- b. Research coordinator:
 1. Responsible for monitoring informed consents
 2. Responsible for reporting all IRB related matters, storing informed consents, and reporting all adverse events to the IRB
 3. Responsible for recruiting and consenting patients for study
 4. Evaluates protocol compliance with the above investigators to ensure data protection and patient confidentiality
 5. Responsible for maintaining regulatory documents
- c. Research Assistant:
 1. Responsible for recruiting and consenting patients for study
 2. Responsible for ensuring data collection from patients
 3. Responsible for escorting patients to the simulator, collecting data and operating the simulator

NCT02782923

4. Monitors and reports to PI and research coordinator the recruitment and retention status as well as adverse events
 5. Facilitates intraoperative data collection and protocol compliance
 6. Responsible for organizing and storing all patient data in a secure location where only authorized personnel have access
 7. Responsible for completing informed consent procedural log
3. Reporting Adverse Events and Unanticipated Problems
- a. Adverse event (AE) grading and attributes
 1. No adverse event or within normal limits
 2. Mild AE, not requiring treatment
 3. Moderate AE, resolved with treatment
 4. Severe AE, resulting in inability to carry on normal activities and required professional medical attention
 5. Life threatening or disabling AE
 6. Fatal AE
 - b. Safety Plan
 1. Adverse events related to study will be detected from follow up visits by the patient and during the post-operative period by the principal investigators, , through physical exam assessment and reviewing x-rays and CT scans of the subject. The investigator will try to determine if the adverse event is related to the research itself or an isolated event using the above criteria.
 2. The research coordinator, will perform safety reviews (collecting adverse events, reviewing them, and reporting them).
 3. The research assistant will score and review questionnaires to determine if a subject's condition has worsened (adverse event), and if determined by the PI to be related to the surgery, the event will be reported by the research coordinator.
 4. All adverse events identified are reported to the PI and the research coordinator
 - c. Plan for periodic or annual reporting of AEs
 1. The IRB will be notified of a serious adverse event and unanticipated adverse event within 24 hours. All other adverse events will be reported annually to the IRB at the time of continuation renewal.
 2. All unanticipated adverse events related to the study will be reported to the IRB in an expedited manner if they are Grade 2 and above in severity. Unanticipated patient deaths are reportable within 7 days. The expedited report sent to other organizations can be copied to the GCRC. The investigator will continue to follow or obtain documentation of the resolution course of such an event.
4. Privacy and Confidentiality
- a. Case report forms and all other documentation collected by the investigators and research coordinator/assistant will not contain subject names. Each subject will be assigned a subject code. The subject code will consist of 8 characters in an alphanumeric combination. The site will maintain the link between the subject code and the names. Primary data collection will be based on source-documented hospital chart reviews, notes on the source worksheets and subject interviews will be performed by study coordinators/researchers or investigators at each clinical site. Data will be stored in individual subject binders and locked in a secure office. Only approved research coordinators/investigators will have access to the data.
5. Assessments

NCT02782923

- a. Safety reviews will be performed monthly by the monitoring entity (the principal investigator). The monitoring entity will be responsible for determining the relationship of an adverse event and the treatment received. Since the PI sees the subjects regularly for follow up visits, he will be familiar with the subjects' outcomes and patient histories, thereby making it easier to detect AEs if they do arise. This plan allows for prompt detection of unanticipated problems involving risks to subjects.
 - b. Monitor the incidents of pseudoarthrosis for both graft groups
6. Criteria for Action
- a. Subject stopping will occur if any adverse events occur that are level 4 or above, or if the subject is unlikely to comply with the follow-up evaluation schedule
 - b. Study stopping will occur if there patients experience persistent pain following the simulator trials
 - c. Study stopping will occur if patient cannot tolerate the simulator due to motion sickness
7. Data Storage and Confidentiality
- a. Case report forms and all other documentation collected by the investigators and research coordinator will not contain subject names. Each subject will be assigned a subject code. The subject code will consist of 8 characters in an alphanumeric combination. The site will maintain the link between the subject code and the names. Primary data collection will be based on source-documented hospital chart reviews, notes on the source worksheets and subject interviews will be performed by study researchers or investigators at each clinical site. Data will be stored in individual subject binders and locked in a secure office. Only approved research coordinators/investigators will have access to the data.

P. OUTCOME MEASURES

Table 1 summarizes all outcome measures and timeline of data collection

NCT02782923

Time Line of Data Collection	Pre-operative	2 weeks FU	6 weeks FU	12 weeks FU	24 week FU (optional)
Patient Demographics Driving History	X				
NRS, PROMIS, NDI Questionnaires	X	X	X	X	X
EQ5D, MJOA, Tandem walk test, 10s grip test, 10s step test (myelopathy patients only)	X			X	X
Clinical/Physical Exam Narcotics Usage	X	X	X	X	X
Driving Performance Data: Simulator Output Data - Total Collisions (TC) - Centerline Crossings (CC) - Off-road Excursions (ORE) - Driving Reaction Time (DRT) Cervical Motion Data: 1. Blind Spot Data a. Unsafe Driving Event (UDE) b. Angular Velocity of Neck Rotation c. Time to initiate lane change d. Maximal axial rotation 2. Cervical range of motion (CROM) 3. Thoracic range of motion (TROM)					
Post-Simulation Questionnaire	X	X	X	X	X
Surgical Data		X			

Table 1: Summary of Outcome Measures

V. REFERENCES

6. Traffic Safety Facts: 2008 Data. (DOT HS 811 162) Washington, DC: US Department of Transportation, National Highway Traffic Safety Administration.

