Degenerative changes in the cervical spine represent an important source of pain and disability in the middle-aged and elderly population (1-3). An estimated 50% of patients with symptomatic cervical disc disease report moderate to severe disability while driving (4). From 1990 to 2000, the total number of cervical spine procedures performed annually more than doubled (2), with recent data showing cervical spine fusions for degenerative cervical disease increased 206% among Medicare beneficiaries from 1992 to 2005 (5). Given the increasing amount of cervical spine procedures being performed annually, it is common for patients to inquire about their ability to drive after surgery.

Driving is a multi-system task that requires cognitive coordination of a variety of complex and coordinated muscular actions. The safe operation of a motor vehicle requires the driver to have adequate range of motion of the extremities to perform steering, braking, reversing and maneuvering of the vehicle. Automobile accidents are a significant cause of death and injury in the

NCT02782923

United States with over ten million accidents every year and human error being a contributing factor in over 90% of all cases (6-9). In the United States, both the Council on Ethical and Judicial Affairs (CEJA) of the American Medical Association and National Highway Traffic Safety Administration (NHTSA) describe the central responsibility of physicians to assess physical and mental impairments that might adversely affect driving (9). The importance of establishing evidence-based guidelines is critical because the term 'fitness to drive' represents a multi-faceted issue with medical, legal and financial implications.

While guidelines for driving following numerous orthopaedic procedures related to the upper and lower extremities have been substantiated by numerous studies (10-17) there is a paucity of quality research in the context of surgical procedures of the spine. A majority of studies related to driving performance after spinal procedures utilize a simple analysis of break reaction time (BRT) or driving reaction time (DRT) (used interchangeably in the literature) to extrapolate driving performance.

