This will be a prospective experimental model study. All non-control study participants will be patients seen by the NYU Department of Spine Surgery faculty group practice and their affiliated private offices. The same care will be provided independent of the patient's willingness to be a part of the study. Patients will be 18 years old or older. There will be no vulnerable subjects in study except for patients older than 65 and patients who are employees or students of NYULMC or NYUSOM. 210 subjects total will be recruited to comprise 7 groups of patients, which was calculated based on power analysis performed using a similar driving simulator study by the authors. Only patients who are able to understand the English language will be allowed to participate in the study due to the nature of the validated questionnaires that will be given to them. The patients will be made known that participation in the study will not affect the standard of care delivered by the investigators. No ethnicities will be prohibited from participating in the study. Males and females will participate in the study as close to a 1:1 ratio as possible. Operative patients who are required to complete research activity for four visits will be compensated. Patients from the CMC office and Madison Orthopedics office will be compensated \$50 for all four visits. Patients who regularly see their physician at farther office sites including but not limited to Seaport Orthopedics and Long Island Branches will be compensated \$100 for all four visits. Optional visits in this study will not be compensated. If all four visits are not completed, patients will be compensated at the end of their participation in accordance with the percent of visits they completed. IRB approved study advertisement will be used to better reach patients.

Payment for Participation

NCT02782923

Subjects will be reimbursed using Greenphire [ClinCard](#) which will allow reimbursement and notification to patients instantly as mentioned in the Study Subjects section above.

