Using Greenphire ClinCard instead of cash or money orders will reduce subjects' drop out. It will provide direct reimbursement to eliminate the financial hurdles that may keep participants from completing study visits. It will provide subjects with instant access to cash via a reloadable debit card. Subjects will be asked to provide their social security number or Alien Registration number, date of birth, and address. This is a requirement for participating in the Greenphire program as this information is needed for federal tax purposes and without this information, subjects cannot sign up the study. We do not anticipate that this will deter patients from enrolling. Optional visits in the study will not be reimbursed.

CONTROL SUBJECTS

40 healthy volunteers will be recruited to undergo one phase of testing using the driving simulator model to serve as a control group. 20 will undergo testing without a collar. 20 will undergo testing using a hard cervical collar vs. soft cervical collar vs. no collar to test limitations of cervical collars on subjects in the driving simulator.

The study will require utilization of the color control group to further elucidate any impact a hard and soft cervical collar will have on ability to drive. Given there will be restricted cervical range of motion when utilizing a cervical collar, the cervical control group will serve two purposes:

- 1) To elucidate whether the cervical range of motion restrictions result in decreased range of motion versus a healthy control population when surveying traffic for blind spots.
- 2) To elucidate whether cervical range of motion restrictions results in decreased driving performance in terms of driving simulator output as compared to a healthy control population.

Volunteers will not receive financial compensation for their participation as only one sitting is required. Compensation will be given to subjects who need to return for follow up visits based on the extent of their travel requirements.

SUBJECT WITHDRAWAL CRITERIA

Patients/subjects are free to withdraw at any time from the study. New subjects will be recruited to replace them.

D. STANDARD OF CARE VS. RESEARCH PROCEDURES

- Unique to Research Procedures
 - o Questionnaires (Neck Disability Index, Numeric Pain Rating Scale, PROMIS , narcotic use survey, driving history survey, post-simulated driving survey, EQ5D, and mJOA)

NCT02782923

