- Measurement of cervical and thoracic axial range of motion using video motion capture technology
- Field of view testing
- 10s grip and release test, 10s step test, Tandem Gait (heel-to-toe) walk*
- Testing of driving performance using a customized driving simulator set-up
- All other procedures are standard of care for all investigators involved

- E. ***These tests tend to be done as part of standard of care identifying myelopathy patients, but in the case it is not performed as standard of care we will perform the tests as a research procedure. Only clinical research staff or non-clinical staff trained to perform the tests will perform the tests. For non-clinical staff who received training, we will still ensure a clinician is in close proximity if help is needed while doing the tests.**

INCLUSION CRITERIA

- *Study Subjects:*
 - Age between 18 and 80 years
 - Indicated for elective cervical spine surgery (including ACDF [single or multi-level], posterior cervical laminectomy and fusion, posterior cervical laminoplasty, posterior cervical foraminotomy, cervical disc replacement) after failing at least 6 weeks of non-operative treatment modalities
 - Valid driving license
 - Regular use of a vehicle
 - Signed consent form
- *Control Subjects:*
 - Age between 18 and 80 years
 - No pre-existing or recent injuries to neck, torso, back
 - No neurologic or systemic debilitating conditions
 - Valid driving license
 - Regular use of a vehicle
 - Signed consent form

F. EXCLUSION CRITERIA

- Significant visual impairment
- Significant debilitating neurological condition with loss of function of one or more extremities
- Recent extremity surgery
- Recent eye surgery
- Previous history of motion sickness, vertigo in simulated settings
- Recent history of chemical or narcotic dependency

G. VULNERABLE POPULATION

Students and faculty of NYU School of Medicine and NYU Langone Medical Center will be recruited as potential control subjects and will be eligible to participate in the study. Students and faculty can voluntarily participate in this study without coercion. The Principal Investigator, Sub-Investigators, and research staff will ensure there are additional safeguards for these subjects. They will

NCT02782923

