emphasize that neither the subjects' academic status, grades, and/or employment will be affected by their decision to participate or not. The principal investigator, sub-investigators, and research staff will ensure that the subjects' record of participation cannot be linked to any type of academic or employee record. The Principal Investigator will ensure that the research design addresses such institutional pressures and preserves the right for subject to refuse participation

Subjects 65 years of age or older will also be recruited as potential subjects and will be eligible to participate in the study if their treating surgeon deems them eligible.

H. POTENTIAL BENEFITS

There are no absolute benefits for the patient or volunteer to complete this study. Patients may potentially become more aware of their post surgical condition and it may affect their ability to drive. Furthermore, from subject participation in the study, there will be a better understanding of the impact cervical spine surgery has on driving performance. This can then allow practitioners to make evidence-based recommendations regarding changes in driving performance in the post-operative period.

I. ADVERSE EVENTS/RISKS

There are no significant risks associated with this study. The driving simulator set-up has been used in three previous studies by the investigators and no adverse events have been reported. The simulated driving scenario can potentially result in motion sickness during the trial. Additionally, there is the possibility that axial rotation of the neck and/or torso may cause the patient discomfort when driving.

J. PROTECTION AGAINST RISKS

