The study subjects will be instructed to inform the research coordinator if they experience motion sickness or discomfort. The simulated trials will be stopped immediately and the study subject will be asked if they would like to complete the trial. If the study subject does not wish to complete the trial, they will have the option to complete the trial at a later date or be removed from the study. The investigators are familiar with the protocol and have utilized this driving simulator in previous studies. For data collection, the research coordinator is knowledgeable in the field of orthopaedic care and clinical research. All personnel have completed CITI training and the investigators have a dedicated staff and nurse to attend to the patient's medical and psychological needs if needed. If patients require medical monitoring, ancillary care, or equipment, patients will be able to seek care in case of an emergency at the NYU-HJD Immediate Care Center, which is open 24/7. The research coordinator, will also be available to patients during regular office hours.

K. INVESTIGATION SCHEDULE AND FOLLOW-UP

Data will be collected regarding individual patient demographics, pre-operative diagnosis, procedure and driving history at the pre-operative and first post-operative time period. Patient-reported outcome instruments (NDI, PROMIS, NRS), physical exam measures, narcotic usage, driving performance measures, a post-simulated driving questionnaire and maximal axial rotation of the neck and torso will be collected at all time points. The EQ5D and mJOA survey will be collected only

NCT02782923

from myelopathy patients at baseline, 3 month, and 6 month. This data will be recorded onto a de-identified data collection sheet by the researchers. The patient data sheets will then be entered into a protected electronic database, while the data sheets will be stored as a back-up until the study is complete. Once the completed database is analyzed and summarized, the results will be presented to the involved participants without any identifiable patient information. Follow-up will be the investigators' routine follow-up at 2 weeks, 6 weeks, 3-months, and 6 month post-operatively. The 6 month routine follow up is unique to myelopathy patients only.

L. CASE REPORT FORMS**1. PRE-OPERATIVE VISIT**

- a. Informed consent
 - i. If informed consent is not obtained at pre-operative visit, the visit will not continue.
- b. Investigator Form (Complete Sections 1-9)

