In addition to the number of unsafe driving events (UDE), driving performance will be evaluated by examining the overall number of collisions, the number of centerline crossings, and the number of off road excursions. Total collisions encompass both “off-road” collisions, when patients veer too far laterally from the computerized boundaries of the driving circuit, and “on-road” collisions, which occur if a patient’s vehicle collides with other cars, pedestrians, hazard work cones, or cyclists designed to be in the program. The number of centerline crossings will be measured by the number of times the patient’s vehicle traverses the centerline crossing over into oncoming traffic. Lastly, “off-road excursions” will be determined by the number of times the patient’s vehicle traversed the lateral road edge and travelled off onto the grass.

Clinical Evaluation

Neck Disability Index (NDI), NRS, PROMIS and clinical data (motor, sensory, pain) will be collected prior to each trial and will serve as measure of functional clinical outcomes. Baseline active painless neck and torso range of motion (axial rotation) will be collected for each patient prior to each trial as described previously. The Dartfish Software has the option of selecting various points in space that will allow computer generated range of motion to be calculated and exported to excel format. The data will then be transferred to a secure data collection file. In addition, field of view evaluation, narcotic use and level of fatigue will be collected prior to each trial.

Demographic Information and Questionnaires

Prior to beginning testing, each patient will complete sections 1-6 of the Investigator Form:

Investigator Form (Sections 1-5)

1. **Demographic Information:** age, gender, ethnicity, height, weight, medical comorbidities, surgical history, history of ocular, neurologic and musculoskeletal conditions, history of

NCT02782923

motion sickness, smoking history, worker's compensation status, current involvement in litigation

2. **Driving Information:** driving experience (years), self-judged frequency of driving, self-reported number of accidents over the last five years, participants' self-judged driving ability with three response categories [poor (1), average (4), and above average (7)]

The research coordinator will complete Sections 6-9 at all testing intervals:

Investigator Form (Sections 6-9)

1. **Surgical Information:** (diagnosis, procedure, complications)

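### No age balance is set for the healthy controls and it is unclear whether their age and driving history are recorded, so the ancillary patient-versus-control comparison is at risk of confounding

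*Protocol*

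**What the plan says.** **The comparison.** Section N (Study Design) states two aims: to find the interval of largest decline, and to find when patients return to baseline. Both compare a patient with his or her own pre-operative result. The same section adds that the information will also be compared with data from healthy volunteers.

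**Who the controls are.** Section C asks for 40 volunteers, each tested at one sitting; 20 of them take part in a collar comparison. The inclusion criteria give controls the same 18 to 80 age range as patients, with a valid licence and regular vehicle use. Section G (Vulnerable Population) says: "Students and faculty of NYU School of Medicine and NYU Langone Medical Center will be recruited as potential control subjects". It then says that subjects aged 65 or older "will be eligible to participate in the study if their treating surgeon deems them eligible". The only characteristic to be balanced is sex, at close to 1:1 (Section C).

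**Who the patients are.** Section II (Background) opens: "Degenerative changes in the cervical spine represent an important source of pain and disability in the middle-aged and elderly population".

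**What is recorded.** Section K says: "Data will be collected regarding individual patient demographics, pre-operative diagnosis, procedure and driving history at the pre-operative and first post-operative time period". Section N says: "Prior to beginning testing, each patient will complete sections 1-6 of the Investigator Form". Section D lists among the research procedures a "narcotic use survey, driving history survey, post-simulated driving survey", without saying who completes them. Section P says: "Table 1 summarizes all outcome measures and timeline of data collection". The columns of that table, like the visits in Section L, are pre-operative or follow-up visits.

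**The concern.** Equal eligibility limits do not give equal age distributions. Nothing in the protocol steers control recruitment towards the ages of the patients, and the one source it names is a medical school and its hospital. If controls turn out younger, or differ in years or frequency of driving, then a patient-control difference in reaction time, neck rotation or driving errors could partly reflect that and not disease or surgery.

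An analysis plan can specify an adjustment, but it cannot change who was recruited, nor recover driving years that were not asked for at a single sitting. Recruitment and data capture are therefore protocol matters, even though the adjustment model is not.

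**Working it through.** **1. Recruitment.** Four statements bear on the age of controls:
- The 18 to 80 range allows almost any age distribution.
- Students and faculty are one source; their share is not given and other sources are not excluded.
- The sentence on subjects aged 65 or older turns on a treating surgeon. A healthy volunteer has none under this protocol, so its meaning for older controls is unclear.
- Sex is balanced; age and driving experience are not mentioned.

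Together these leave the control age distribution to chance.

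**2. Recording.** Evidence that controls may not be covered: Sections K and N speak of patients, Section L lists only pre-operative and follow-up visits, and Table 1 has only such columns. Evidence that they may be covered: the driving history survey in Section D is not limited to patients, and the protocol uses the word patient loosely. Section C says "210 subjects total will be recruited to comprise 7 groups of patients", and the group list in Section N gives 5 x 30 + 20 + 40 = 210, so the 40 controls are inside that count. Eligibility screening must also establish each control's age, licence and vehicle use, but not driving years, frequency or accidents. The question is open.

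**3. Size of bias.** The bias would be the age gap multiplied by the change in outcome per year of age. The documents give neither. Age and driving experience could also act in opposite directions. No figure is derived.

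**4. Precision cost of adjusting (illustration only).** This assumes that age is recorded and adjusted for, so it does not measure confounding.

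Inputs from the protocol: one surgical group of 30; 40 controls. Assumed: age gap 10 or 20 years, within-group age SD 10 to 15 years, two-sided 5%, 80% power.

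Variance inflation of the group effect: VIF = 1 + p(1-p)(gap/SD)^2. With p = 30/70, p(1-p) = 0.245. With no gap, the noncentral t distribution on 67 degrees of freedom gives a detectable difference of 0.687 residual SD. With a gap, this is multiplied by the square root of VIF.

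| Gap (years) | Age SD | VIF | Detectable difference (SD) |
|---|---|---|---|
| 0 | any | 1.000 | 0.687 |
| 10 | 15 | 1.109 | 0.723 |
| 10 | 12 | 1.170 | 0.743 |
| 10 | 10 | 1.245 | 0.766 |
| 20 | 15 | 1.435 | 0.823 |
| 20 | 12 | 1.680 | 0.890 |
| 20 | 10 | 1.980 | 0.966 |

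The 40 controls are collar-free only if the 20 collar volunteers are each tested in all conditions, which Section C does not settle. Under a three-way split, 20 + 20/3, or about 27, controls have collar-free runs. The no-gap figure is then about 0.757 SD (54 degrees of freedom). Several outcomes are event counts, so all t-based figures are approximate.

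**The case against.** The strongest reply is that this is mostly silence. Patients and controls share the same age range and licence rule. Section G exists to protect students and employees from pressure and is not a sampling plan; it speaks of potential controls, includes faculty, and goes on to say that subjects aged 65 or older will be recruited. Adjustment may be in an analysis plan that is not shown. The detectable differences rest wholly on assumed gaps. All of this stands, and it limits the point to a risk. It does not answer the point, because neither recruitment nor a missed item can be repaired in the analysis.

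Several stronger readings are tempting, and the documents do not support them:
- *Controls will be young.* The share of students is not stated, and faculty may be older.
- *Control demographics are not collected.* The wording is loose enough to include controls, and a driving history survey is listed without restriction.
- *Older volunteers are excluded.* The treating-surgeon sentence is unclear for them, but it excludes nobody.
- *The main aims are confounded.* Both are within-patient.
- *A false-positive rate can be attached.* That needs an age effect per decade, which the documents do not give.
- *Collared runs dilute the healthy reference.* Section C makes them the test condition against a healthy control population, and no passage proposes pooling them.

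**Conclusion.** The concern holds as a risk to one comparison. The protocol plans to set patients against healthy controls, but does nothing to align the two on age or driving experience and does not make clear that the data needed for adjustment will be taken from controls. Calling the comparison ancillary is an inference: the protocol does not rank it, but neither stated aim depends on it. Imbalance and non-collection are both possible and neither is established. The only figures that can be given are the illustrative precision losses. With 40 collar-free controls, the detectable difference would rise by about 5% to 12% for a 10-year gap (0.723/0.687 to 0.766/0.687) and by about 20% to 41% for a 20-year gap (0.823/0.687 to 0.966/0.687). The change should be made, because it is cheap and cannot be made after the controls have been tested.

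**What to change.** Amend Section C (Control Subjects) in two ways.

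1. Frequency-match controls to the age distribution of the enrolled surgical patients in broad bands, for example 18-44, 45-64 and 65-80, with band sizes proportional to the patients. The cut at 65 is the protocol's own. Students and faculty count only towards their own band. Clarify how the sentence in Section G on subjects aged 65 or older applies to volunteers.
2. State that every control completes the demographic and driving-information sections of the existing Investigator Form at the single sitting, and add that sitting to the form list in Section L and to Table 1.

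Matching to all surgical patients together reduces the age difference against each single procedure group but does not remove it, and differences can remain within a band. Adjustment for age is therefore still needed; its model can stay with the analysis plan. It would also help to say whether the 20 collar volunteers are crossed over or split, since that decides whether the collar-free reference is 40 or about 27.

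The cost is slower recruitment of older controls and one short existing form per control. No extra subjects are needed.
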